The project will embed bCBT into PCMHI programs using existing VHA providers. A total of 225 Veterans diagnosed with an anxiety disorder will be recruited from three VAMCs. Eligible Veteran participants will be randomized to a bCBT or to an Enhanced Usual Care (EUC) condition. A professionally diverse set of PCMHI providers will be invited to deliver bCBT. Providers will receive bCBT training and support to embed treatment into their existing practice setting. Veterans randomized to bCBT will receive 4 – 9 sessions based upon treatment response (50% reduction in GAD-7) by session 4. Veterans will also be offered the choice of receiving bCBT in-person or through VVC-H. EUC participants will receive 4 brief monthly check-in calls from study staff and a note placed in their medical record alerting their provider to the presence of significant anxiety symptoms. BCBT treatment and EUC check-in calls will end at 4 months.

The project leverages VA stakeholders at all levels to improve alignment of the work with VA and Veteran initiatives. Clinical outcomes will provide justifications or cautions to inform future evidence-based psychotherapy (EBP) programs. If positive, data will be used to assist VA leadership in the expansion of EBPs and VVC-H in PCMHI. For example, should the project produce robust clinical outcomes - next steps would involve a non-research / demonstration project in one or two VISNs where the project team will train and support a wider group of providers in the delivery of brief CBT for anxiety. The project team will use the training program and clinical intervention materials as well as lessons learned from the proposed HSR&D IIR to support and enhance brief CBT delivery in a non-research context.

List of Abbreviations

Provide a list of all abbreviations used in the protocol and their associated meanings.

ACOS – Associate Chief of Staff
AUDIT-C – Alcohol Use Disorders Identification Test
bCBT – Brief Cognitive Behavioral Therapy
CAPRI – Compensation and Pension Record Interchange
CBT – Cognitive Behavioral Therapy
CCI – Charlson Comorbidity Index
CoE – Center of Excellence
Co I – Co-Investigator
CPRS – Computerized Patient Record System
DSM-5 – Diagnostic and Statistical Manual of Mental Disorders version 5
DSMB – Data Safety Monitoring Board
EBP – Evidence Based Practice
ERS – Expectancy Rating Scale
EUC – Enhanced Usual Care
FE – Formative Evaluation
GAD – Generalized Anxiety Disorder
GAD-7 – General Anxiety Disorder (7-item scale)

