3.0 Objectives

- Describe the study's purpose, specific aims, or objectives.
- State the hypotheses to be tested.
- Indicate the relevance to Veterans and the VA

The primary hypothesis is that anxiety outcomes, as measured by the GAD-7, and quality of life, measured by the SF-12 will be superior at 4-, 8-, and 12-month follow up for patients who are assigned to receive bCBT vs. EUC.

Primary Aim: To determine whether anxiety symptoms (GAD-7) and quality of life (SF-12) differ as a function of the intervention (bCBT for anxiety vs. EUC) at 4-, 8-, and 12-month follow-ups.

Secondary Aims: (Prediction of bCBT response and VVC-H use (bCBT group only)): A) To identify factors associated with bCBT response, namely whether bCBT is effective for specific anxiety disorders (e.g. generalized anxiety, panic, social phobia) and whether number of sessions received, and treatment engagement are critical to outcomes. B) To identify Veteran demographic and clinical factors associated with VVC-H use.

Exploratory Aims: A mixed-methods formative evaluation, informed by RE-AIM QuEST, will collect data related to Reach (#of Veterans receiving bCBT and VVC-H), Effectiveness (bCBT and VVC-H impact), Adoption (# of providers using bCBT and VVC-H), and Implementation (provider bCBT program fidelity and VVC-H potential). Data will be collected from qualitative interviews with Veterans and providers and integrated with quantitative data from provider surveys and chart reviews of bCBT and VVC-H use. With the ORD supplement to the main project, [name] will leverage the diverse Veteran populations included in the multisite

parent study (Houston, San Antonio, and New Orleans VA MCs) to understand barriers to treatment and research access for African American and Hispanic Veterans.

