forwarded via encrypted email to a study-consented provider. Provider and clinic personnel will schedule the patient for an initial treatment session. Participants and clinicians will work collaboratively to determine the modality of treatment (i.e., traditional in-person visits, VVC-H, or a mixture). Clinicians will be encouraged to offer 4 weekly treatment sessions but may alter the intensity or "dose" of treatment, based on Veteran anxiety response scores and/or provider/patient decision to discontinue treatment. For completers, the final treatment "dose" may include between 4 and 9 sessions over a course of up to 4 months. Clinicians will be asked to complete the GAD-7 during treatment sessions to assess treatment response (regular GAD-7 administration is consistent with bCBT and measurement-based care). Data on treatment sessions will be documented using template CPRS clinician notes to facilitate clinician documentation, allowing the study team to monitor and extract important treatment information during and after the trial.

Treatment completion will be defined as 4 or more sessions over the 4-month treatment period. A 50% reduction in baseline GAD-7 scores will indicate treatment response^{5,6}. Providers and patients will collaboratively determine whether additional bCBT skill sessions are needed based on treatment response. A 50% reduction in anxiety symptoms was chosen, based on prior work and evidence from other studies^{7,8,9}. This response criterion also appropriately classifies responders with variable baseline anxiety levels.

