During active treatment, clinicians will be asked to discuss anxiety symptoms and response with participants as part of the treatment process. Providers will be encouraged to deliver bCBT as long as it remains appropriate for any given patient. If a patient is discovered to have additional needs that make the use of bCBT inappropriate, the clinician can opt to seek additional or alternative care for the patient. The presence of severe depression, substance abuse, and comorbid PTSD could all require the clinician to change or add treatments. At the end of the 4-month treatment period, clinicians will be encouraged but not required to discontinue treatment. For patients who reach the response criterion, clinicians will introduce the potential for treatment discontinuation. For patients who do not reach the targeted anxiety goal by the final session (4th session), clinicians will work with the patient to determine whether additional sessions would be helpful. The provider will have the option to continue care or refer the patient to other therapies that are not a part of the research study based on their clinical judgment.

Figure 1. Response to bCBT and Determination of Treatment Ending

The proposed bCBT intervention (See Appendix 5G) uses a patient-centered approach to increase engagement while addressing the mental health needs of anxious Veterans. A bCBT provider manual and a patient workbook provide structure and increase Veteran participation. The patient workbook will be made available both in hard copy and in an electronic version. The workbook includes intervention session information and worksheets, along with homework assignments to engage Veterans during VVC-H sessions and facilitate between-session activities. The bCBT intervention skill modules use CBT-based techniques established in our prior trials^{10, 11} and flexibly apply these skills to improve anxiety symptoms and overall quality of life (see Table 1). All participants take part in an initial session where they receive psychoeducation on anxiety and the bCBT treatment approach, set goals, and begin self-monitoring. Three core skill sessions focused on relaxation, cognitive, and exposure techniques follow. Participants who do not show treatment response at session 4 will be offered up to 4 additional cognitive and/or exposure skill sessions. All participants receive a final wrap-up session to review gains and plan for maintenance of skills.

Table 1. bCBT Intervention Overview

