bCBT Treatment Variables: Treatment delivery variables will include Intensity/Dose, Session Delivery Format: Intensity/dose of bCBT will be defined as the total number of sessions attended. Delivery format (VVC-H vs. in-person) will be documented for each session to allow us to examine the impact of VVC-H use on outcomes. These data will be collected via note templates and chart review procedures. Working Alliance will be assessed using patient and therapist report forms of the Working Alliance Inventory - Short Form (WAI-S).²⁶ The WAI-S (Appendix 8I) consists of 12 items and yields an overall score. VVC-H variables of interest including Veteran comfort receiving in-person VHA care, confidence using video technology, and logistic access to video technology will also be assessed at baseline.

Secondary Measures: To better understand factors that may contribute to participant treatment response, the protocol includes brief assessments for the following: social support (Appendix 8E and Appendix 8F) and attachment style (Appendix 8K). Careful consideration has been taken into selection of the measures, as not to add any undue burden on participants.

ORD Supplement Measures: In addition to baseline measures included in the parent study, Veteran participants will be asked to complete additional quantitative measures at baseline (see Appendix 6F, Diversity Supplement). Racial/Ethnic Identification will be measured using the first open-answer item of The Multigroup Ethnic Identity Measure (MEIM)²⁷, created to distinguish between particular ethnic groups, using 1 item. Perceived Discrimination will be assessed using the 9-item Perceived Discrimination Scale (PDS)²⁸ daily discrimination subscale. The measure evaluates daily discrimination experiences based on the participant's race, ethnicity, religion, physical appearance, or other characteristic. Anxiety Disorder Phenotype will be assessed using the 18-item Anxiety Sensitivity Inventory (ASI)²⁹. The measure has 3 subscales: physical concerns, cognitive concerns and social concerns. It is valid and reliable in clinical samples, and the subscales have empirical construct validity.³ Perceptions of Mental Health Treatment Access will be assessed using the 32-item Barriers to Access to Care Evaluation scale (BACE)³⁰. It has demonstrated good reliability and validity in measuring key barriers to access to mental health care for adults.

Initial Telephone Screening Assessment:

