To compare changes in anxiety symptoms between the two groups over time, we will use a longitudinal, mixed-model analysis containing terms for the intercept, treatment, time, and interaction between time and treatment. In separate analyses, we will compare changes in quality-of-life between the two groups over time using a similar mixed-model approach. The mixed-model analysis will allow us to nest patients by site. Any baseline characteristics found to be significantly different between bCBT and EUC will be included in the model, as will any differences in mental health service use. The four time points (baseline, 4-, 8-, and 12-month) will allow us to assess the immediate impact of treatment and the longer-term retention, improvement, or decay in outcomes. The treatment effect will measure differences between the intervention and control groups at baseline, and the time effect will measure whether there was an overall change over time in the outcome. The term of most interest will be the interaction between time and treatment, which will indicate whether there is a difference over time between the two groups. The use of the random-coefficient model will allow us to fit a line for each participant using his/her available data, including participants with missing values, and maximize the power to detect differences.

Secondary Analyses: Prediction of bCBT response and VVC-H use:

We will run two logistic regression analyses using only data from participants who received bCBT. In analysis 1, we will identify characteristics that predict response to treatment as defined as a reduction of 50% on the GAD-7. Predictor variables will include: baseline anxiety severity (GAD-7 score), presence of specific anxiety diagnoses (GAD, Panic, Social Anxiety, Other), medical comorbidities, and brief CBT-related factors (number sessions received and treatment engagement). In analysis 2, we will identify characteristics associated with VVC-H use. VVC-H

use will be classified as any (one or more VVC-H sessions) or none. Predictor variables will include: age, distance to VA facility in miles, medical comorbidities, depression and PTSD (presence or absence), and Veteran self-reported comfort receiving in-person VHA care and confidence using video-based services and technology.

Implementation Analyses (Exploratory):

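### Aim 2A uses total sessions to predict 50% GAD-7 response, but missing that same 50% mark at session 4 is what triggers extra sessions, so the coefficient is not a dose effect

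*Protocol*

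**What the plan says.** Section 3.0 of the Protocol asks, for the bCBT arm, "whether number of sessions received, and treatment engagement are critical to outcomes". Section 5.6 (Secondary Analyses) answers with a logistic regression in bCBT recipients to find characteristics that "predict response to treatment as defined as a reduction of 50% on the GAD-7". The predictors are baseline GAD-7, specific anxiety diagnoses, medical comorbidity and "brief CBT-related factors (number sessions received and treatment engagement". Section 5.5 fixes the count: "Intensity/dose of bCBT will be defined as the total number of sessions attended". Core, optional and wrap-up sessions are therefore pooled.

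The number of sessions is itself tied to response. The Abstract gives 4 to 9 "sessions based upon treatment response (50% reduction in GAD-7) by session 4". Section 5.1 says: "Participants who do not show treatment response at session 4 will be offered up to 4 additional cognitive and/or exposure skill sessions". For patients who do meet the criterion, clinicians raise the option of stopping. The dose for completers "may include between 4 and 9 sessions over a course of up to 4 months", and clinicians may change it "based on Veteran anxiety response scores and/or provider/patient decision to discontinue treatment".

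The available SAP text covers only the primary aim and adds nothing on this model.

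**The concern.** Outcome and dosing rule share one instrument and one threshold. A patient with eight sessions is likely to be one who had not responded at session 4, and early non-response tends to predict later non-response. A higher count then goes with less response even if the extra sessions do nothing, or do some good. This is confounding by indication. Baseline GAD-7 cannot remove it, because the confounder is status during treatment.

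A second force acts the other way. Patients who stop after one to three sessions have low counts, and if they do worse the coefficient moves up. The documents fix the size of neither force.

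At stake is what Aim 2A says about extending bCBT beyond the core sessions in a setting where brevity is the design premise. It could make extra sessions look harmful, useful or irrelevant without evidence for any of these.

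**Working it through.** **Figures in the plan.** The plan gives no figure for this coefficient. Its sample size for the secondary models (section 5.6) reproduces: 87 x 1.25 = 108.75, taken as 109; 109 / 0.75 = 145.3, taken as 145. Its statement of 80% power for an odds ratio of 2.5 cannot be confirmed or refuted, since the base rate and predictor distribution are not given; it is not disputed here. Patients analysed after 25% attrition: 145 x 0.75 = 108.75, or 109.

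**What the rule does to the count.** Take 4 core sessions plus wrap-up = 5 for anyone who reaches session 4. If extended patients have 1-4 extra sessions (uniform, mean 2.5) and 50-80% of session-4 non-responders accept, non-responders average 5 + 0.5 x 2.5 = 6.25 to 5 + 0.8 x 2.5 = 7.0 sessions, against 5 for responders. A gap of 1.25-2.0 sessions arises from the rule alone.

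**Simulation (all inputs assumed).**
- Improvement at session 4 and at the outcome visit is bivariate normal, correlation 0.5 or 0.7.
- Response at session 4 is 25% or 40%; at outcome 35, 45 or 55% before any shift.
- 25% stop after 1-3 sessions, with outcome shifted by 0, -0.25 or -0.5 SD.
- Uptake of extra sessions is 50% or 80%, 1-4 sessions each; sessions are cut off at the outcome visit.
- Model: logit P(response) = a + b x sessions; odds ratio per session = exp(b).
- Scenarios per shift: 2 x 2 x 3 x 2 = 24. Odds ratios come from 200,000 patients, error rates from 400 trials of 109. Ranges are minimum to maximum.

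| True effect | Early stoppers | Total-session odds ratio | False significant result |
|---|---|---|---|
| None | unrelated to outcome | 0.86-0.95 | 'less response' 6-39% |
| None | 0.25 SD worse | 0.91-1.01 | 'less response' 1-16% |
| None | 0.5 SD worse | 0.96-1.08 | 'less' 0-4%, 'more' 0-11% |
| 0.1 SD per extra session | unrelated to outcome | 0.94-1.03 | |
| 0.1 SD per extra session | 0.5 SD worse | 1.05-1.17 | |

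The nominal rate in each direction is 2.5%. Values of 0.96-1.03 occur both with no effect (third row) and with a real benefit (fourth row), so the coefficient does not separate the two.

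**Sensitivity.**
- With no effect and unrelated stopping, a session-4-to-outcome correlation of 0.3 gives 0.94-0.97 and 6-10% false 'less' results; zero correlation gives about 1.00.
- All 8 planned predictors, with engagement as a separate covariate, leave 0.86-0.95 and 8-40%.
- If engagement is coded as 4 or more sessions, the session odds ratio is 0.59-0.87 across all three stopping assumptions.
- A separate model on the GAD-7 scale (baseline mean 14.5, SD 3, limited to 10-21; mean improvement 5 points by session 4; 25% early stopping; 70% uptake; baseline-adjusted) gives 0.89 with no effect, and a false 'less response' result in 23% of trials at n = 109 and 31% at n = 145. Varying uptake over 30-100% and improvement over 3-7 points gives 0.84-0.94.

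**Landmark alternative** (patients who reach session 4; extra sessions as predictor; adjusted for baseline and session-4 GAD-7). With no effect it gives 0.99-1.03 if extension depends only on session-4 status; with the 0.1 SD benefit, 1.19-1.29. Patients: 109 x 0.75 = 81.75, about 82. The standard error of the log odds ratio is 0.18-0.28, so the odds ratio detectable with 80% power is exp(2.80 x 0.18) = 1.66 to exp(2.80 x 0.28) = 2.19. Power for the 0.1 SD benefit is 11-25%.

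**The case against.** The strongest defence has four parts.

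*It is a prediction model.* Section 5.6 speaks of prediction and section 3.0 of associated factors. But section 3.0 also asks whether session number is critical, and section 5.5 labels the count as dose. A count known only when treatment ends is not a baseline predictor either.

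*The rule is soft and the inputs are assumed.* Extra sessions are offered, not imposed, and the documents give no uptake, stopping or session-4 response rates. This stands as a limit on size: neither sign nor magnitude is established. Discretion weakens the link to response without breaking it.

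*The landmark can be further from the truth.* If the decision to extend also follows prognosis not captured by session-4 GAD-7 (assumed log-odds 0.5 per SD), then with no dose effect the landmark gives about 0.79-0.90, against 0.84-0.91, 0.90-0.96 and 0.95-1.03 for total sessions as early stoppers worsen. This stands as a warning about the remedy. Total sessions come closer to 1 only because opposing biases cancel. With engagement coded as 4 or more sessions, the planned model gives 0.54-0.75 under the same assumption.

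*The consequence is modest.* No decision in the protocol hangs on Aim 2A, and the assessment schedule labels 4 months as post-treatment. Also, 109 reflects one-year attrition, so more patients may be available at 4 months. All fair. A larger sample does not reduce the bias and makes a false finding more likely (31% against 23% above).

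**Conclusion.** The concern holds. That the count depends on session-4 response follows from the protocol's own rules. That this biases the coefficient needs only that session-4 status predicts the outcome. The net direction depends on how early stoppers fare, how closely session-4 status tracks the outcome visit and how engagement is coded. With engagement as a separate covariate or omitted, null odds ratios run from 0.86 to 1.08 per session at correlations of 0.5-0.7; with engagement coded as 4 or more sessions they are always below 1. All these sizes are illustrative. The missing cut-off on the count is a lesser matter and the main bias does not need it. This is a secondary, non-randomized analysis, and the bCBT versus EUC comparison is untouched. It should be corrected before analysis.

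**What to change.** 1. Name the visit that defines response, for example the 4-month assessment, and count only sessions dated before it.
2. State that the total-session coefficient will not be interpreted as a dose effect. This step costs nothing and matters most.
3. Define treatment engagement so that it is not a recoding of session count.
4. Estimate the association of extra sessions with response in a landmark analysis: patients who reach session 4, adjusted for baseline and session-4 GAD-7 from the treatment notes.
5. If core sessions attended (1-4) are reported, call them a marker of retention. With early stoppers 0.5 SD worse and no dose effect they give a false odds ratio of 1.39-1.45 per session.

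State the limits of step 4: about 82 patients, 80% power only for odds ratios of about 1.7-2.2 per extra session, still observational, and biased downward if extension follows prognosis that the session-4 score misses.

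The cost is protocol and SAP wording. Session counts from note templates and chart review (section 5.5) and in-session GAD-7 scores (section 5.1 and Table 5) are already planned. The landmark analysis loses early stoppers and anyone without a recorded session-4 score, and clinicians are asked, not required, to record one.

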Other Demographic and Clinical Data: Demographic data will include age, gender, ethnicity, income, marital status, education, employment, and distance from the VA and/or CBOC¹⁰. Diagnosis of anxiety disorders, PTSD, and depression will be based on the MINI structured interview²¹. Each diagnosis will be dichotomized and coded as present/absent. PTSD severity will be assessed using the PTSD Checklist-Civilian Version (PCL-5²²), a standardized self-report rating scale that corresponds to DSM-5 symptoms of PTSD and possess strong psychometric properties. Medical complexity will be calculated using the Charlson Comorbidity Index (CCI) as defined by VA database extractions for the 12 months prior to the baseline date. The Charlson score has been widely used in the literature for assessing morbidity and mortality^{23,24}. Psychotropic medications will be collected through VINCI databases following procedures used

in the team's prior work^{10,11,25}. Medication tracking will include information on start date of medication, dose, and days-supply. Medication use will be coded for presence or absence and changes in type or dosage. We will monitor medications use in both bCBT and EUC groups through database extraction after the 12-month assessments to allow us to determine whether assignment to bCBT affected receipt of medications. Mental health service use: Mental health service use will be monitored for each participant to allow us to control for non-bCBT mental health service use. We will collect data via review of VA medical records as well as from a self-report non-VA service-use questionnaire (Appendix 6G). We will use CDW to capture data on emergency room visits and hospitalizations and will compare the frequency and types of such visits between arms (and between in-person and VVC-H bCBT encounters) quarterly. We will involve clinical leadership and the IRB if there are between-group differences in these safety measures.

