Step 3: Provider Inflation Factor. The bCBT sample size was then inflated to account for the intraclass correlation due to clustering of patients within providers⁴³. We also will adjust the sample sizes for both the bCBT and EUC groups to account for attrition. Because only participants receiving bCBT are assigned to a provider, we first determined the average number of bCBT patients per provider (87 bCBT patients/25 providers = 3.5 patients per provider). To account for clustering in the bCBT group, the number of bCBT patients is inflated by the factor $[1 + (\bar{m} - 1) c]$, where \bar{m} is the average number of bCBT patients per provider and c is the correlation among patients seen by the same provider. Based on the sample size of 87 bCBT patients and an assumed correlation among patients of .10⁴³, our inflation factor is 1.25 ($87 \times 1.25 = 109$). Finally, to account for attrition, we assumed an attrition rate at 1 year of 25% ($109 \times (1/0.75) = 145$) gives 145 bCBT patients. A similar clustering inflation factor was not used for the EUC group, as no providers are assigned. Attrition rate of 25% was assigned to the EUC group ($58 \times (1/0.75) = 78$), rounded to 80 for randomization. The final number of randomized patients equates to 225 (145 bCBT and 80 EUC).

Secondary Aims:

Prediction of bCBT response and VVC-H use (bCBT group only). To assess predictors of bCBT response and VVC-H use, at least 10 events per variable in the logistic-regression models are needed to have unbiased estimates of the sample variance of the regression coefficients⁴⁴. No sample-size calculations were conducted for secondary aim, but SAS[®] proc power (version 9.4)⁴⁵ indicated a sample of 145 is adequate for 80% power to test odds ratio of 2.5, and conservative estimates for sample size and assumptions necessary to run the analyses suggest the project will be appropriately powered for 10 variables⁴⁶. Secondary analyses will include 8 variables for aim 2A (bCBT response; model #1) and 8 variables for aim 2B (VVC-H prediction; model #2).

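### The Aim 2B model is said to have 8 predictors but only 7 are named, and access to video technology, which is assessed at baseline, is not among them

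*Protocol*

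**What the plan says.** Protocol 5.6 (Sample Size and Power Calculations, Secondary Aims) fixes the size of both secondary models: "Secondary analyses will include 8 variables for aim 2A (bCBT response; model #1) and 8 variables for aim 2B (VVC-H prediction; model #2"). The predictors of VVC-H use are listed earlier in 5.6, under Secondary Analyses, analysis 2. The list begins "Predictor variables will include: age, distance to VA facility in miles, medical comorbidities, depression and PTSD (presence or absence") and ends with "Veteran self-reported comfort receiving in-person VHA care and confidence using video-based services and technology".

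Protocol 5.5 (bCBT Treatment Variables) describes what is collected: "VVC-H variables of interest including Veteran comfort receiving in-person VHA care, confidence using video technology, and logistic access to video technology", all assessed at baseline. The first two appear in the analysis 2 list and the third does not.

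The SAP's data analysis plan covers the primary aim and lists no Aim 2B predictors, so it does not settle the matter.

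**The concern.** The stated count and the named list disagree by one. The collected variable that is not named is the measured factor closest to the outcome, because a Veteran without workable access to the technology can hardly have a video session, whatever the preference.

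Two things are at stake. First, Aim 2B asks which factors go with VVC-H use, and the list as written would leave the most proximal measured one unexamined. Second, if access drives use and is related to confidence, age or distance, part of its association may show up in their odds ratios. The protocol intends the results to inform expansion of VVC-H, so readers will take the adjusted odds ratios as pointers to what should be addressed.

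The ambiguity is itself a problem. One analyst could work from the list and another from the count, and the predictor set could then be settled after the data are seen.

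**Working it through.** **1. Check the counting rule on the companion model.** Count each named item or diagnosis as one variable. For Aim 2A (5.6, analysis 1): GAD-7 score (1) + four anxiety diagnoses (4) + medical comorbidities (1) + sessions and engagement (2) = 8. This reproduces the stated 8.

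**2. Apply the same rule to Aim 2B.**

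| Named in 5.6, analysis 2 | Count | Running total |
|---|---|---|
| Age | 1 | 1 |
| Distance | 1 | 2 |
| Medical comorbidities | 1 | 3 |
| Depression | 1 | 4 |
| PTSD | 1 | 5 |
| Comfort with in-person care | 1 | 6 |
| Confidence with video | 1 | 7 |

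The result is 7 against a stated 8. Depression and PTSD count separately because 5.5 says "Each diagnosis will be dichotomized and coded as present/absent". Treating them as one item gives 6. Splitting confidence into services and technology gives 8, but 5.5 treats confidence as a single variable. Adding access gives 7 + 1 = 8.

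**3. Events per variable.** Protocol 5.6 asks for at least 10. The number that limits a logistic model is the smaller outcome class: EPV = min(users, non-users) / predictors. The bCBT arm has 145 patients and the analysis takes only those who received bCBT, so 145 is a ceiling and the smaller class is at most 72.

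| VVC-H use (assumed) | Smaller class | EPV, 7 predictors | EPV, 8 predictors |
|---|---|---|---|
| 50% | 72 | 72/7 = 10.3 | 72/8 = 9.0 |
| 30% or 70% | 0.3 × 145 = 43.5 | 6.2 | 5.4 |

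Eight predictors at 10 each need 80 events. If only users counted as events, 80/145 = 55% would have to use VVC-H, but non-users would then number at most 65. Ten variables, the number 5.6 says the sample supports, would need 100.

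**4. Illustration of the possible shift (all inputs assumed).** 200,000 simulated patients, about 75% with access, true confidence odds ratio 1.5 per SD. The table gives the confidence odds ratio when access is left out.

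| Access odds ratio | Correlation 0 | Correlation 0.3 | Correlation 0.5 |
|---|---|---|---|
| 1 | 1.51 | 1.50 | 1.50 |
| 2 | 1.49 | 1.59 | 1.66 |
| 4 | 1.46 | 1.67 | 1.80 |

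The correlation is between confidence and the latent variable behind access. With access in the model the estimates are 1.50 to 1.53. There is no upward shift if access has no effect or is uncorrelated with confidence. Age and distance were not part of this illustration.

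**5. Shift against sampling error.** At n = 145 and 50% use, the standard error of a log odds ratio per SD is at least 1/√(145 × 0.5 × 0.5) = 0.166. The largest shift above is ln(1.80/1.5) = 0.182, about 1.1 standard errors.

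**The case against.** The best defence is that nothing shows access to be excluded. The list is introduced with wording that does not close it, and the count of 8 suggests that access may be the intended eighth variable, lost in drafting. That stands: the text fails to name access, and it does not show a decision to leave it out. The stated aim also speaks of demographic and clinical factors, and access is neither. But the same is true of comfort and confidence, which are listed.

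A reader might infer that effects of access will be reported as effects of age, distance or confidence. The documents do not support that. It needs access both to affect use and to be correlated with those predictors, and no figure is given for either. For age, a shift need not be an error at all. If older Veterans use video less because they lack access, the age association is genuine and access is the pathway. Aim 2B seeks associations, not direct effects. Any shift of the size illustrated would also be hard to tell from chance in 145 patients.

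Nor is the model the only source on barriers. The formative evaluation interviews 10 fully engaged Veterans who opted for VVC-H and 10 who declined it, though interviews do not replace a named predictor in the quantitative model.

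Finally, adding a predictor strains a small model. That stands as a cost, but 5.6 already commits to 8.

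**Conclusion.** The point holds as a discrepancy with a practical consequence. Section 5.6 counts 8 predictors and names 7, under a rule that reproduces its own count for Aim 2A. Access is the natural eighth, since 5.5 names it beside the two VVC-H variables that are listed. Followed as written, the list leaves access out of the model of VVC-H use.

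Confounding of the other odds ratios is possible but not demonstrated. The range of 1.6 to 1.8 around a true 1.5 rests wholly on assumed values (access odds ratio 2 to 4, correlation 0.3 to 0.5) and cannot be offered as the trial's expected bias.

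The events-per-variable ceiling of 9.0 with 8 predictors does not depend on those assumptions. It follows from 145 patients and falls as use moves away from 50% or as patients who received no bCBT drop out of the analysis set.

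**What to change.** In Protocol 5.6, Secondary Analyses, name logistic access to video technology as the eighth predictor of analysis 2 and word the list as complete. Sections 5.5 and 5.6 then agree, and the predictor set is fixed before the data are seen.

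In the same edit, revise the events-per-variable statement under Secondary Aims: 8 predictors cannot reach 10 events each in the smaller outcome class with 145 patients. Either say so and treat the model as exploratory, or specify penalised estimation such as Firth's. Penalisation also helps if few VVC-H users lack access, when cells may be sparse and ordinary maximum likelihood unstable.

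As a clerical matter, add comfort, confidence and access to the Baseline Assessment text in 5.5 and to the baseline column of Table 4, since neither shows them now.

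The cost is a phrase in the list, a sentence on events per variable, and a table row. No new data are needed. The statistical price is one coefficient more than the seven named, with the ceiling falling from 10.3 to 9.0 events per variable, though the total is no more than the 8 already stated.
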